# 7.3 Phase II

Schedule of pembrolizumab, cryoablation, mDCs, and Prevnar13 will be based on the tolerability findings of the run-in phase

# 7.4 Apheresis

Patients will undergo apheresis on Cycle 1, Day 1, from which monocytes will be collected by immunomagnetic isolation and cultured *in vitro* under GMP conditions to generate mature DCs (mDCs). The generated mDCs will be frozen and stored until ready for use. Autologous mature dendritic cells (mDCs) will be prepared for administration into the cryoablated tumor. At a minimum, mDCs necessary for 2 injections (30-60  $\times 10^6$  per injection) will be manufactured. Additional mDCs and lysate will be stored for potential retreatment and immune monitoring assays. If insufficient mDCs are available for treatment, the total mDCs should be split into two doses, and the treating physician may determine whether to continue with protocol treatment or take the patient off study.

NOTE: If first mDC production attempt does not yield any releasable mDCs, then one additional apheresis may be attempted.

# 7.5 Cryoablation, mDC administration, and Prevnar13 administration

Each patient will undergo percutaneous cryoablation within 36 hours of pembrolizumab treatment on Cycles 2 and 3. (Generally, this will take place on Cycle 2, Day 2, and Cycle 3, Day 2. However, it is acceptable that cryoablation could be performed on Cycle 2, Day 1, and Cycle 3, Day 1.) Two distinct metastatic lesions will be treated with cryoablation, one during Cycle 2, and the other during Cycle 3. Our general cryoablation technique has been previously described (McMenomy et al. JVIR 2013; 24:207-213). Due to the extended length of the procedure, requiring the patient to lie still (expected duration 45 minutes), sedation will be managed by the Department of Anesthesia. Using ultrasound and/or CT guidance, a cryoprobe will be placed in the index melanoma lesion. Research biopsies (6 18-gauge cores) will be obtained immediately prior to freezing the tumor. The lesion will be treated using a conventional freeze-thaw- freeze cycle with the endpoint being the generation of an iceball that measures at least 75% of the diameter of the index tumor but may encompass the entire tumor with a margin of normal tissue.

Following the freezing procedure, the cryoprobe will be actively warmed and then withdrawn. After the lesion has thawed, a 22 G needle will be placed under ultrasound or CT-guidance into the ablated portion of the lesion. The mDC will be administered through this needle over different areas of the cryoablated region and then flushed with 1ml of sterile saline. Prevnar13® will be injected into the ablated portion of the lesion after administration of mDCs. The patient will be transferred to the recovery area and monitored for 2 hours following cryoablation and DC injections for acute toxicity. Given the elevated risk of solid organ cryoablation, patients undergoing ablation of such tumors will be admitted to the hospital for overnight observation, including hematologic assessment prior to discharge.

# 7.6 **Duration of therapy**

Patients may remain on pembrolizumab treatment for up to two years. After two years, patients go to event monitoring and may receive pembrolizumab off protocol at the discretion of the treating provider.

# 8.0 Dosage Modification Based on Adverse Events

# 8.1 Treatment schedule modifications in patients based on adverse events

Patients will be evaluated by the study team prior to each dose of pembrolizumab for an adverse event check. Determination will be made if the adverse event is treatment-related (possible, probable or definite), i.e. a toxicity (see Section 10; Adverse event monitoring and reporting). If any adverse event has occurred, then the treatment schedule will be modified as in Section 8.2. If an adverse event occurs during Cycle 2 that requires treatment to be held, then omit pembrolizumab for Cycle 3 and resume pembrolizumab with Cycle 4.

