# 8.2 Treatment schedule modifications for pembrolizumab.

Adverse events (both non-serious and serious) associated with pembrolizumab exposure may represent an immunologic etiology. These adverse events may occur shortly after the first dose or several months after the last dose of treatment. Pembrolizumab must be withheld for drug-related toxicities and severe or life-threatening AEs per Table 8.21 below. See Section 9.0 for supportive care guidelines, including use of corticosteroids.

CTCAE System/Organ/Class		a 1	
(SOC)	Adverse Event	Grade	Action
General disorders and administration site conditions	Infusion related reaction	2	Hold all protocol treatment until Grade 0-1 If AE does not resolve to Grade 0-1 within 3 weeks, then permanently discontinue all protocol treatment
		3-4	Permanently discontinue all protocol treatment
Respiratory, thoracic and mediastinal disorders	Pneumonitis	2	Hold all protocol treatment until Grade 0-1 If AE does not resolve to Grade 0-1 within 3 weeks, then permanently discontinue all protocol treatment
		3-4	Permanently discontinue all protocol treatment
Renal and urinary disorders.	Acute kidney injury or Chronic kidney disease	2	Hold all protocol treatment until Grade 0-1 If AE does not resolve to Grade 0-1 within 3 weeks, then permanently discontinue all protocol treatment
		3-4	Permanently discontinue all protocol treatment
	All Other Nonhematologic Events	3	Hold all protocol treatment until Grade 0-1 If AE does not resolve to Grade 0-1 within 3 weeks, then permanently discontinue all protocol treatment
		4	Permanently discontinue all protocol treatment

Table 8.21	Dose Modification Guidelines for Drug-Related Adverse Events
------------	--------------------------------------------------------------

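### After a Cycle 2 toxicity hold, Section 8.1 and Table 8.21 give pembrolizumab instructions that do not fit together and leave the second cryoablation and cell injection unsettled

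*Combined protocol and SAP*

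**What the plan says.** Section 8.1 opens with a general rule: "If any adverse event has occurred, then the treatment schedule will be modified as in Section 8.2". It then adds a rule for one cycle. The trigger is worded "If an adverse event occurs during Cycle 2 that requires treatment to be held", and the action that follows from it is "then omit pembrolizumab for Cycle 3 and resume pembrolizumab with Cycle 4". That sentence names pembrolizumab and nothing else, and it attaches no condition to the Cycle 4 restart.

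Section 8.2 is headed as a pembrolizumab section, and its lead-in speaks of that drug: "Pembrolizumab must be withheld for drug-related toxicities and severe or life-threatening AEs per Table 8.21 below". The table it points to acts on more than that drug. Its hold rows are Grade 2 infusion reaction, pneumonitis or kidney event, and Grade 3 for other nonhematologic events. Each of them reads "Hold all protocol treatment until Grade 0-1", and a second sentence in the same row sets the limit: "If AE does not resolve to Grade 0-1 within 3 weeks, then permanently discontinue all protocol treatment". The table has no exception for Cycle 2 and no fixed restart cycle.

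Pembrolizumab is not the only treatment due in Cycle 3. Section 7.5 states: "Two distinct metastatic lesions will be treated with cryoablation, one during Cycle 2, and the other during Cycle 3". Each procedure includes mDC and Prevnar13 injection, and its timing is tied to the drug: "Each patient will undergo percutaneous cryoablation within 36 hours of pembrolizumab treatment on Cycles 2 and 3". On Schedule -1 (Section 7.22) pembrolizumab is not given in Cycles 2 and 3 at all.

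**The concern.** Two investigators following the protocol in good faith could manage the same Cycle 2 toxicity differently. One could skip the Cycle 3 pembrolizumab dose after an event that has already settled, while the other gives it. One could plan a Cycle 4 restart for a patient whom the other has taken off treatment. Neither can tell from Section 8.1 whether the second lesion should be frozen and injected when the dose that times the procedure has been omitted.

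Three things are at stake: the safety of a patient with an active toxicity, consistency of exposure among patients in the response analysis, and the proportion receiving both intratumoral injections (Section 16.32). Cycle 2 is the first cycle that combines pembrolizumab with the procedure on Schedule 1, so a hold there arises at the first test of the combination.

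**Working it through.** The plan gives no figure to reproduce on this point. The check compares the texts and adds calendar arithmetic.

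**Inputs.** Cycle length is 21 days, with a possible extension of Cycle 1 only (Section 7.0). The 3-week limit comes from Table 8.21, and the omission at Cycle 3 and restart at Cycle 4 from Section 8.1. Take Cycle 2 Day 1 as day 1 and ignore visit windows.

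**Calendar.**
- Cycle 3 Day 1 = 1 + 21 = day 22.
- Cycle 4 Day 1 = 22 + 21 = day 43.
- A Cycle 2 event has its onset on day d, with d from 1 to 21.
- The table does not say when its 3 weeks begin. Counted from onset, the limit is day d + 21. This runs from 1 + 21 = day 22 to 21 + 21 = day 42, always before day 43.
- Counted instead from the first withheld Cycle 3 dose (an assumption), the limit is 22 + 21 = day 43, which is Cycle 4 Day 1.

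On either count, by the time Section 8.1 says to restart, the table has already allowed resumption or reached the point of ending treatment.

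**Side by side, for the hold rows.**

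| Course of the event | Section 8.1, read alone | Table 8.21 |
|---|---|---|
| Grade 0-1 before day 22 | Cycle 3 pembrolizumab omitted, restart on day 43 | Hold already over on day 22 |
| Unresolved on day 22, Grade 0-1 within the limit | Same | Hold in force on day 22, lifted later |
| Unresolved at the limit | Same | All components ended for good |

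The first row diverges by one pembrolizumab dose. In the second row both texts can be followed for pembrolizumab. In the third, one text restarts treatment and the other has stopped it, unless the table is taken to override.

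**Cycle 3 procedure.** While the table's hold is in force, the procedure is held too. Once it lifts, or if it lifted before day 22, Section 8.1 is silent on the procedure. Section 7.5 places the procedure within 36 hours of a dose that Section 8.1 has removed. So in the first two rows the texts do not settle whether or when the second lesion is treated.

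**Schedule -1.** No pembrolizumab is planned for Cycle 3 and it is already due again at Cycle 4 (Section 7.22). The Section 8.1 instruction therefore changes nothing there, and only the table gives guidance.

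**Effect per patient on Section 16.32.** Total enrolment is 33 if Schedule 1 is carried forward, or at most 39 if Schedule -1 is (Section 16.2). If all of them start treatment, one patient whose second injection depends on the reading shifts the proportion by 1/33 = 3.0 percentage points, or 1/39 = 2.6.

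**The case against.** The best defence is that the two passages are cumulative. Section 8.1 sends every adverse event to Section 8.2 before it mentions Cycle 2, and its Cycle 2 sentence applies only to an event that needs a hold, a status the table assigns. On that reading the table governs holding, resolution and stopping, and Section 8.1 merely adds which pembrolizumab dose is skipped. A patient whose event does not resolve is stopped under the table and never reaches the restart. The extra skip may also be deliberate, since its effect on pembrolizumab in Cycle 3 resembles Schedule -1.

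Much of this stands. The non-resolution conflict exists only if the Cycle 2 sentence is read on its own terms, and the table rows that call for immediate permanent discontinuation do not conflict with Section 8.1. The defence fails on two counts. The text does not say that the Cycle 4 restart is subject to the table. And even the cumulative reading leaves an early-resolving event with a table hold that has ended beside a dose that is still omitted, and leaves the Cycle 3 procedure without a rule.

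A reader might go further in three ways that the documents do not support:
- One might infer that Section 8.1 directs the Cycle 3 cryoablation and injection to go ahead without pembrolizumab. It does not; it is silent, and the table explicitly holds everything. This is a gap beside an explicit rule.
- One might infer that dose-limiting toxicity assessment is compromised. Under Sections 7.0 and 16.1, whether an event qualifies turns on its grade, attribution and resolution, not on whether the Cycle 3 dose was given.
- One might infer that the feasibility endpoint lacks a rule for a missed second injection. Section 16.32 supplies it: such a patient stays in the denominator and is not counted as having received both. What varies with the reading is whether the injection is given.

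**Conclusion.** The concern holds in a limited form. For a Cycle 2 event in a hold row, the two texts differ when the event resolves before Cycle 3 Day 1. They differ again when it remains unresolved at 3 weeks, but only if Section 8.1 is read literally. Whether and when the second cryoablation and injection take place is unclear however that sentence is read. This is an inconsistency in a safety instruction, and it deserves correction for that reason and for consistent exposure.

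Its size across the trial cannot be given, because the documents state no expected rate of Cycle 2 holds. The per-patient effect is one pembrolizumab dose for an early-resolving event, and up to about 3 percentage points on a descriptive proportion that carries no decision rule. The sample-size calculation in Section 16.2 does not use any of these inputs, and the primary endpoint's denominator, all who started at the continuation level, is unchanged. The conclusion assumes nominal 21-day cycles. The early-resolution divergence and the gap over the Cycle 3 procedure do not depend on when the 3-week clock starts.

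**What to change.** Reconcile Sections 8.1 and 8.2, together with 7.22 and 7.5, into a single instruction for an adverse event in Cycle 2 that requires a hold. It should state:
- which treatment components are held;
- whether the Cycle 4 restart is subject to the table's resolution and discontinuation conditions, and from what day the 3 weeks are counted;
- whether the Cycle 3 omission applies when the event has resolved before Cycle 3 Day 1;
- what happens to the Cycle 3 cryoablation, mDC and Prevnar13, and what their timing refers to if pembrolizumab is not given;
- how the instruction works on Schedule -1.

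The heading and lead-in of Section 8.2 should match the scope of its table. Which clinical rule applies in each case is for the sponsor to decide. The cost is protocol wording; sample size, endpoint definitions and planned analyses are untouched.

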# 8.2 Treatment schedule modifications for pembrolizumab.

Adverse events (both non-serious and serious) associated with pembrolizumab exposure may represent an immunologic etiology. These adverse events may occur shortly after the first dose or several months after the last dose of treatment. Pembrolizumab must be withheld for drug-related toxicities and severe or life-threatening AEs per Table 8.21 below. See Section 9.0 for supportive care guidelines, including use of corticosteroids.

CTCAE System/Organ/Class		a 1	
(SOC)	Adverse Event	Grade	Action
General disorders and administration site conditions	Infusion related reaction	2	Hold all protocol treatment until Grade 0-1 If AE does not resolve to Grade 0-1 within 3 weeks, then permanently discontinue all protocol treatment
		3-4	Permanently discontinue all protocol treatment
Respiratory, thoracic and mediastinal disorders	Pneumonitis	2	Hold all protocol treatment until Grade 0-1 If AE does not resolve to Grade 0-1 within 3 weeks, then permanently discontinue all protocol treatment
		3-4	Permanently discontinue all protocol treatment
Renal and urinary disorders.	Acute kidney injury or Chronic kidney disease	2	Hold all protocol treatment until Grade 0-1 If AE does not resolve to Grade 0-1 within 3 weeks, then permanently discontinue all protocol treatment
		3-4	Permanently discontinue all protocol treatment
	All Other Nonhematologic Events	3	Hold all protocol treatment until Grade 0-1 If AE does not resolve to Grade 0-1 within 3 weeks, then permanently discontinue all protocol treatment
		4	Permanently discontinue all protocol treatment

Table 8.21	Dose Modification Guidelines for Drug-Related Adverse Events
------------	--------------------------------------------------------------

# 9.0 Ancillary Treatment/Supportive Care

# 9.1 Full Supportive Care

Patients should receive full supportive care while on this study. This includes blood product support, antibiotic treatment, and treatment of other newly diagnosed or concurrent medical conditions. All blood products and concomitant medications such as antidiarrheals, analgesics, and/or antiemetics received from within 28 days before the study treatment administration until 30 days after the final dose will be recorded in the medical records.

9.11 Antiemetics

Antiemetics may be used at the discretion of the treating physician.

9.12 Non-Steroidal Anti-Inflammatory Drugs (NSAIDS)

NSAIDs use limited to standard non-prescription doses.

9.13 Blood Products and Growth Factors

Blood products and growth factors should be utilized as clinically warranted and following institutional policies and recommendations. The use of growth factors should follow published guidelines of the American Society of Clinical Oncology: Recommendations for the Use of WBC Growth Factors: American Society of Clinical Oncology Practice Guidelines Update. Journal of Clinical Oncology 2015;33:3199-3212..

# 9.2 Suggested supportive care measures for the management of adverse events with potential immunologic etiology

Subjects should receive appropriate supportive care measures as deemed necessary by the treating investigator. Suggested supportive care measures for the management of adverse events with potential immunologic etiology are outlined below. Where appropriate, these guidelines include the use of oral or intravenous treatment with corticosteroids as well as additional anti-inflammatory agents if symptoms do not improve with administration of corticosteroids. Note that several courses of steroid tapering may be necessary as symptoms may worsen when the steroid dose is decreased. For each disorder, attempts should be made to rule out other causes such as metastatic disease or bacterial or viral infection, which might require additional supportive care. The treatment guidelines are intended to be applied when the investigator determines the events to be related to pembrolizumab.

Note: if after the evaluation the event is determined not to be related, the investigator does not need to follow the treatment guidance (as outlined below). Refer to Section 8.0 for dose modification.

It may be necessary to perform additional procedures such as bronchoscopy, endoscopy, or skin photography as part of evaluation of the event.

- Pneumonitis:
  - For Grade 2 events, treat with systemic corticosteroids at 0.5 -1 mg/kg of prednisone or equivalent. Monitor O2 saturations. When symptoms improve to Grade 1 or less, steroid taper should be started and continued over no less than 4 weeks.
  - For Grade 3 events. Rule out infectious events, but do not hold steroids while doing so. Consider hospitalization, start steroids at 2 mg/kg of prednisone or equivalent. Monitor O2 and administer oxygen as needed. Once symptoms

improve to grade 1 or less, steroid taper should be started and continued over no less than 4 weeks. Consider bronchoscopy, to evaluate for infection.

- For Grade 4 events, patients should be hospitalized in an intensive care unit, and started on high dose IV steroids at 1 gram of methylprednisolone. Rule out infectious etiology, but do not hold steroids while doing so. Consult Pulmonology and patients should undergo bronchoscopy. Administer additional anti-inflammatory measures, as needed.
- Add prophylactic antibiotics for opportunistic infections in the case of prolonged steroid administration.

#### • Diarrhea/Colitis:

Subjects should be carefully monitored for signs and symptoms of enterocolitis (such as diarrhea, abdominal pain, blood or mucus in stool, with or without fever) and of bowel perforation (such as peritoneal signs and ileus). Any patients with these symptoms should immediately undergo CT of the abdomen to rule out bowel perforation.

- All subjects who experience diarrhea/colitis should be advised to drink liberal quantities of clear fluids. If sufficient oral fluid intake is not feasible, fluid and electrolytes should be substituted via IV infusion. For Grade 2 or higher diarrhea, consider GI consultation and endoscopy to confirm or rule out colitis.
- For Grade 2 diarrhea/colitis, lasting >one week patients should be started on budesonide 12 mg QD. Additionally infectious etiologies should be ruled out. Do not hold steroids while ruling out infection. For patients who do not respond to budesonide or have progressive diarrhea, these patients should be started on systemic steroids at 0.5-1 mg/kg of prednisone or equivalent.
- For Grade 3 diarrhea/colitis, patients should be started on budesonide at 12 mg daily (if not already started) and 2 mg/kg of prednisone or equivalent. IF no response within 3 days, patient should be hospitalized and started on IV steroids (methylprednisolone 500 mg-1000mg/daily). Beware of rebound diarrhea.
- For Grade 4 diarrhea/colitis patients should be hospitalized and started on 1 gram of methylprednisolone daily, and 12 mg budesonide QD, for up to 3 days (then reduce to 2 mg/kg of prednisone or equivalent) and consult with GI immediately. Patients who do not respond to steroids, may consider infliximab (under direction of GI). Patients who respond initially to high dose IV steroids can be transitioned to high dose oral steroids (2mg/kg). Beware of rebound diarrhea.
- For all patients, when symptoms improve to Grade 1 or less, steroid taper should be started and continued over no less than 4 weeks.
- Type 1 diabetes mellitus (if new onset, including diabetic ketoacidosis [DKA]) or ≥Grade 3 Hyperglycemia.
  - For T1DM or Grade 3-4 Hyperglycemia
    - Insulin replacement therapy is recommended for Type I diabetes mellitus, treat based on grade of hyperglycemia as below.
    - For Grade 3 Hyperglycemia- Consider hospitalization, insulin therapy is required. Monitor glucose closely, and refer to Endocrinology for further management.
    - For Grade 4 hyperglycemia associated with metabolic acidosis or ketonuria. Hospitalize patient (consider admission to an ICU), immediate insulin therapy is necessary, and refer to endocrinology for further management.

• Evaluate patients with serum glucose and a metabolic panel, urine ketones, glycosylated hemoglobin, and C-peptide.

#### • Hypophysitis:

- For Grade 2 events, treat with corticosteroids 0.5mg/kg. When symptoms improve to Grade 1 or less, steroid taper should be started and be rapidly tapered to physiologic steroid dosing provided patient remains asymptomatic (some patients may require a slower taper). Replacement of appropriate hormones may be required as the steroid dose is tapered. Refer to Endocrinology for further management.
- For Grade 3-4 events, treat with high dose (1-2 mg/kg) of prednisone or equivalent). When symptoms improve to Grade 1 or less, rapidly taper to physiologic steroid dosing provided patients remains asymptomatic (some patients may require a slower taper). Replacement of appropriate hormones may be required as the steroid dose is tapered. Refer to endocrinology for further management.

## • Hyperthyroidism or Hypothyroidism:

Thyroid disorders can occur at any time during treatment. Monitor patients for changes in thyroid function (at the start of treatment, periodically during treatment, and as indicated based on clinical evaluation) and for clinical signs and symptoms of thyroid disorders.

- Grade 2 hyperthyroidism events:
  - Non-selective beta-blockers (e.g. propranolol) are suggested as initial therapy.
- Grade 3-4 hyperthyroidism
  - As above- Additionally patients should be hospitalized and may need possible thyroid suppression therapy. Patients should be immediately referred to an endocrinologist for treatment.
- Hypothyroidism (TSH <10)
  - o Asymptomatic- no intervention needed, continue to monitor TFTs
  - Symptomatic- thyroid replacement indicated.
- Hypothyroidism (TSH >10)
  - Thyroid replacement indicated.
- Hepatic:
  - For Grade 2 events, monitor liver function tests twice weekly until returned to Grade 1 and/or baseline values.
    - Treat with oral steroids at 1 mg/kg of prednisone or equivalent. Once levels return to grade 1 or less, begin steroid taper and taper over at least 4 weeks.
  - For Grade 3:
    - Rule out other causes (i.e., progressive disease)
    - Asymptomatic treat with 1-2 mg/kg of prednisone or equivalent
    - Symptomatic- treat with IV steroids, 500 mg of methylprednisolone or equivalent, Consider hospitalization. Once resolved to grade 1 taper steroids over at least 4 weeks.
  - For Grade 4:
    - Rule out other causes (i.e., progressive disease)

- Hospitalize, and treat with intravenous corticosteroids (1 gram methylprednisolone) for 24 to 48 hours. Once stable, may switch to oral high dose steroids.
- When symptoms improve to Grade 1 or less, a steroid taper should be started and continued over no less than 4 weeks.
- For patients who are refractory to steroids, consider hepatology consult and starting mycophenolate.

